B.2. Overview of study approach. In the proposed study, 75 HCV-infected genotype-1 infected PWIDs eligible for on-site HCV treatment with Zepatier will be recruited from diverse community settings, and randomized to either aDOT (n=25), aDot + gamification (n=25), or TAU (n=25). We will measure adherence with pill counts in both arms and with the a-DOT interface in the a-DOT arm. All subjects will be treated with the standard regimens for 12 weeks based on subtype, baseline NS5a polymorphisms and treatment history. For this study we will not enroll patients taking Ribavirin.

- G1a: Treatment-naïve or PegIFN/RBV-experienced without baseline NS5A polymorphisms: Zepatier for 12 weeks
- G1b: Treatment-naïve or PegIFN/RBV-experienced: Zepatier for 12 weeks

B.3. Setting: Montefiore and Einstein Division of Substance Abuse (DoSA). DoSA is a clinical, research, and teaching division of Einstein’s Department of Psychiatry and Behavioral Sciences. DoSA operates a comprehensive substance abuse treatment program providing pharmacotherapy and related services to about 4200 adults (≥ 18 years) with current narcotic addiction (typically heroin). The primary focus is treatment of opiate dependence with methadone, and the average methadone pick-up schedule is 5 times per week. At present, DoSA operates three large clinics in three Bronx communities. The treatment paradigm relies on integrating general and HCV- and HIV-related medical, substance abuse, and mental health services under one roof. Multiple RCTs have been conducted in DoSA. Both recruitment and research visits will occur at DoSA. With [name] (HCV Medical Director), participant recruitment and private office space for research visits will be ensured. We have established treatment programs and/or partnerships with three additional programs: **syringe exchange program (New York Harm Reduction Educators - NYHRE), federally-qualified health center (Comprehensive Health Care Center), homeless shelter (The Living Room), and a methadone maintenance treatment program (Montefiore Wellness Centers).**

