B.4. Participants. Most DoSA patients are Hispanic (59%) or black (24%), male (62%), and live under the federal poverty line (81%). Mean age is 47 years. Approximately 65% (n=2730) are HCV-infected, and 75% of those have chronic HCV (n=2048); 70% have genotype-1 (n=1434), and 80% of those are HIV-negative (n=1147). We will check HBV serologies for all patients and exclude those who are HBsAg positive. We will monitor those that are HBN core Ab positive and treat as medically appropriate.

Table 1. Inclusion and Exclusion Criteria

Inclusion Criteria	Exclusion Criteria

 • HCV-infected (HCV RNA test above the limit of quantification at baseline) • Genotypes/Subtypes: G1a or G1b • Eligible for HCV treatment per 2016 AASLD/IDSA guidelines • Willing to receive HCV treatment on-site at DoSA clinics • Health care provider decision to treat patient with Zepatier-based therapy based on 2016 AASLD/IDSA guidelines • Using illicit drugs (either opiates, cocaine, or benzodiazepenes) within the last 6 months • Age 18 or older • Able to provide informed consent • English or Spanish speaking 	
 • Known hypersensitivity (allergy) to elbasvir, grazoprevir • Pregnant or breast-feeding

B.5. Recruitment. Recruitment (as with other successful studies conducted in this setting) will be both active and passive; for active recruitment DoSA medical providers will inform HCV-infected subjects about the study and assist with referral, and for passive recruitment subjects will self-refer. Self-referred subjects will meet with their provider to determine whether starting HCV treatment is appropriate. In addition to DoSA, we will recruit from three other settings which serve PWIDs: 1) primary care  IRB NUMBER: 2016-7215

Care Center; 2) syringe exchange program – New York Harm Reduction Educators; 3) homeless shelter with on-site HCV care – The Living Room. Potential subjects will be tested on-site with rapid HCV test kit (ongoing NYC DOHMH and CDC rapid testing project). Determination of chronic hepatitis C will be done at Montefiore Medical Center through Roche TaqMAN assay, and HCV NS5A Drug Resistance Assay through LabCorp as a send-out.

Determination of eligibility.

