B.7. Assignment to Interventions. Participants will be assigned to either control or treatment arms via computer-generated random numbers. The mechanism used to generate the random numbers will be REDCap, which provides a blinded randomization feature for participant assignment. The allocation sequence will be generated and input into REDCap by in-house Biostatisticians. The Research Assistant will enroll participants without prior knowledge of allocation sequence.

B.8. Treatment arms: a-DOT and TAU. HCV care will be delivered on-site at three clinical settings (methadone clinic, community health center, and homeless clinic) and via linkage to either the methadone program or community health center for subjects recruited at the syringe exchange program. Central pharmacists will deliver the study medications to the respective clinics. In both arms (a-DOT and TAU), Zepatier will be dispensed monthly at the clinical visit by the provider (2 bi-monthly packs).

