B.9.6. Subject Compensation. Subjects will receive \$25 for each research visit and \$10 for each returned blister pack. Subjects randomized to the a-DOT arm (n=50) will receive additional incentives based on adherence measured at monthly visits: \$10 for 50% adherence; \$20 for 80% adherence; and \$30 for 95% adherence. For the subjects further randomized to the a-DOT + gamification intervention, the second-most adherent participant will receive an additional \$35 incentive, while the top-most adherent patient will receive a \$50 incentive at their subsequent study visit. Should the top two participants be tied, the participant with the most adherent time of dosing will be awarded the first-place prize. In total, participants may earn up to \$453, including metrocards and incentives.

B.9.7. Data Management/Confidentiality. Data will be stored with study ID codes in locked filing cabinets, separate from name-based files, which will be stored in a different locked cabinet. All study information and name-based information will be kept in separate, password protected, HIPAA compliant REDCap databases online. All name-based information will be destroyed at the end of the study, while study-ID-based information will be deleted if participants decline to allow storage of their records for future research of 50 years. All participants will be informed of the data management and confidentiality plan at the time of consent to participate.

B.10. Analytic plan.

First, the success of randomization will be checked by comparing the a-DOT and TAU groups on key variables, such as age, gender, race, HCV viral load, advanced liver disease, psychiatric, and active drug use. Continuous variables will be compared between study arms using the Student's t or Wilcoxon test, and

categorical variables will be compared using chi-square or Fisher's exact tests. Variables that are not equally distributed will be included in multivariate models if they are also associated with the study outcome.

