Adherence to Zepatier (continuous measure) will be determined as the amount of medication taken by each patient during the first 12 weeks will be expressed as a percentage (with a 0-100% range) of the target dose. Subjects will be classified as "adherent" if they receive at least 80% of the total dose of Zepatier. Subjects who receive less than 80% of the total dose of Zepatier will be classified as "non-adherent." Analyses using self-reported adherence will also be conducted. Self-report is more accessible to clinicians than pill count, and there is added value in performing analogous analyses using the self-report measure.

Because adherence will be measured two ways (pill counts and self-report) *concordance correlation coefficients* will be calculated and performed to evaluate agreement between the measures. We will also test if the means of the two measurements are equal. Because adherence will be measured monthly, mixed-effects linear models for repeated measures that account for within-subject correlation will be used. In addition, we will examine the adherence data using a dichotomous cut-off (adherence \geq 80%), and determine the proportion of subjects who were sometimes, always, or never adherent during the 12-week treatment period. To this end, separate analyses will be performed for pill count and self-report adherence data.

For subjects randomized to the a-DOT arm, association between active drug use during treatment and the continuous adherence will be tested using Student's t or Wilcoxon signed rank test, depending on normality of the data. Bivariate analysis of dichotomous adherence data with categorical variables will be performed with chi-square and Fisher exact tests. We will conduct multivariate logistic regression analyses based on findings from the univariate analysis, but recognize that our modest sample size will limit such models.

Based on our pilot data, if we conservatively assume that 80% of subjects in the a-DOT will achieve \geq 80% adherence (v. 50% in the TAU arm), we will have $>$ 80% power to find a statistically significant difference. With the application of mixed-effects logistic regression to the repeatedly measured binary adherence outcome, power will be greater than 80% no matter how large the within-subject outcome correlation or intraclass correlation (ICC).

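### Covariates are selected by undefined tests of baseline imbalance and outcome association; a short fixed set should be named in advance for the adherence mixed linear model

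*Combined protocol and SAP*

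**What the plan says.** Section B.10 (Analytic plan) opens by comparing a-DOT with TAU on "key variables, such as age, gender, race, HCV viral load, advanced liver disease, psychiatric, and active drug use". The comparison is by significance test: t or Wilcoxon for continuous variables, chi-square or Fisher for categorical ones. It then gives the covariate rule: "Variables that are not equally distributed will be included in multivariate models if they are also associated with the study outcome". Both conditions must be met. The section does not say what p-value or difference counts as unequal, or what counts as associated. The mixed-effects models for monthly adherence, described next, list no covariates.

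The design does not supply balance on these factors. Section B.7 says "Participants will be assigned to either control or treatment arms via computer-generated random numbers" and describes no stratification. Section B.5 says "In addition to DoSA, we will recruit from three other settings which serve PWIDs", which makes four settings, but setting is not among the variables named for the baseline check. Active drug use is. Table 3 (section B.9.2) schedules urine toxicology at week 0. It does not list recruitment setting, although setting is known once a subject is recruited.

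**The concern.** Under proper randomisation a baseline test can detect only chance. Its p-value says little about whether a factor matters for the outcome, and in 75 subjects it misses imbalances large enough to shift the estimate when the factor is prognostic. Requiring an observed outcome association as well means the final model is settled only after outcome data are seen, from an open-ended list and with no stated cut-offs.

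Two things are at stake. One is precision: adjustment for a prognostic factor pays off whether or not the factor happens to be imbalanced, and this rule forgoes it in most trials. The other is conditional validity: in trials where a prognostic factor is moderately imbalanced but not flagged, the unadjusted comparison is off-target.

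**Working it through.** **Inputs from the documents.** Three arms of 25 (B.2), so pooled a-DOT 50 v. TAU 25; d=0.6 and ICC up to 0.5 (B.10); pill counts at weeks 4, 8 and 12 (Table 3); seven variables named for the baseline check (B.10). **Assumed:** two-sided 5% for the arm comparison, p<0.05 for both conditions of the rule, and all R² and correlation values.

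**1. The plan's own figure.** Pilot pooled SD = √[(20×12² + 18×20²)/38] = 16.3, so d = 10/16.3 = 0.61, as stated. The variance of a mean of three measures, in SD units, is (1+2×0.5)/3 = 0.667. SE = √[0.667×(1/50+1/25)] = 0.200. Power = Φ(0.6/0.200 − 1.96) = Φ(1.04) = 85.1%. The claim of more than 80% reproduces for 50 v. 25. For 25 v. 25 the same formula gives 73.8%.

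**2. How often the rule adjusts.** With seven independent variables tested at 5%, at least one looks imbalanced in 1 − 0.95⁷ = 30.2% of trials. The second condition cuts this sharply. In simulations of 2,500 trials per scenario (50 v. 25, seven covariates, two of them prognostic with R² of 5-20% each):
- at least one covariate enters in 6-11% of trials (2-3% when none is prognostic);
- a given prognostic covariate enters in about 2-6%;
- with the imbalance test loosened and R² of 10% and 5%, at least one enters in 14% (p<0.10) or 27% (p<0.20).

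**3. Precision recovered.** With one adherence value per subject and d=0.6, the same simulations gave:

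| Analysis | Power |
|---|---|
| Unadjusted | 67-69% |
| Stated rule | 67-68% |
| Pre-specified, total R² 10% | 71% |
| Pre-specified, total R² 15% | 74% |
| Pre-specified, total R² 30% | 82% |

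**4. Gain in the planned repeated-measures setting.** Multiply the variance in step 1 by (1−R²)×[1 + q/(73−q−1)], where q is the number of covariate terms, 73 = 75−2, and R² is the share of variance in subject-mean adherence explained. For example, q=1 and R²=10% give 0.9×(1+1/71) = 0.913, and power Φ(3.0/√0.913 − 1.96) = 88.1%.

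| R² | q=1 | q=2 | q=4 |
|---|---|---|---|
| 0 | 84.6% | 84.1% | 83.0% |
| 10% | 88.1% | 87.7% | 86.7% |
| 20% | 91.5% | 91.1% | 90.3% |

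Break-even is R² = 1 − 1/[1 + q/(72−q)] = q/72: 1.4% for one term, 2.8% for two and 5.6% for four (three for setting, one for toxicology).

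**5. Type I error.** Overall error under the rule was 3.9-5.0%. In simulations with one binary factor, an arm difference of 15 points or more arose in about 22% of trials. Where that difference went unadjusted, the error was about 6-7% if the factor's correlation with adherence was 0.3, and about 7-10% if it was 0.5. The separate simulation runs differed within those ranges.

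**The case against.** The strongest reply is that the loss is not documented. Nothing in the documents says how much adherence varies with setting or baseline drug use. Table 1 requires every subject to be "Using illicit drugs (either opiates, cocaine, or benzodiazepenes) within the last 6 months", which narrows the drug-use contrast. Aim 4 expects no link between use during treatment and adherence under a-DOT. If R² is near zero, adjustment costs a little power. This stands, and it is why the gain is given as a range. It is not decisive: Aim 4 concerns use during treatment and only the a-DOT arm, and the downside is small.

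It is also fair that the low entry rate depends on a cut-off the plan never states. With an imbalance test at p<0.20 the rule adjusts for something in about a quarter of trials. The missing threshold is, however, part of the defect.

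The protocol describes the study as a pilot meant partly to supply effect sizes for later trials. That limits the consequences, but an effect estimate carried forward also benefits from a fixed model.

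A reader might extend the point to the logistic models in B.10, where the plan says "We will conduct multivariate logistic regression analyses based on findings from the univariate analysis". The documents do not support that. The sentence sits in the paragraph on predictors of adherence within the a-DOT arm, where no between-arm imbalance condition can apply, and it goes on to concede that the sample size limits such models. The precision argument here concerns the linear adherence model.

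**Conclusion.** The point holds in this form: covariates are chosen by post-randomisation tests with no stated thresholds, no adjustment set is fixed, and under a conventional p<0.05 reading the rule recovers almost none of the precision available from adjustment while leaving moderate chance imbalances uncorrected.

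The size of the loss is conditional. At d=0.6, 50 v. 25 and ICC 0.5, a single fixed covariate moves power from 85.1% to between 84.6% (R²=0) and 91.5% (R²=20%). With four terms the loss is about two points if none is prognostic.

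Two stronger readings should be resisted. The rule does not inflate overall type I error; the error rises only conditionally, where a prognostic imbalance goes unadjusted. Nor does the plan ignore drug use: it is on the screening list, so setting is the clearer omission.

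The figures assume the p<0.05 cut-offs, no dropout, and in the multi-covariate simulations independent, normally distributed covariates.

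**What to change.** In B.10, delete the imbalance-plus-association rule and report baseline characteristics by arm descriptively, without significance tests. State that the mixed linear model for adherence will include a short fixed covariate set regardless of observed balance:
- week-0 urine toxicology, any positive v. none, with the handling of a missing result specified;
- recruitment setting, if kept to few terms (for example methadone clinic v. other), with setting added to the data collection in Table 3.

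Present the unadjusted estimate alongside as a sensitivity analysis.

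The cost is SAP wording and one or two degrees of freedom. Toxicology is already collected, and setting is known at enrolment. If neither factor is prognostic, two terms lower power from 85.1% to 84.1%. Using all four settings plus toxicology would lower it to 83.0%, which is the reason to keep the terms few.

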- 1. To determine in a randomized trial whether HCV treatment delivered via a-DOT (Zepatier with and without ribavirin) provided on-site at community treatment programs during a 12-week study period is more efficacious than self-administered HCV treatment for enhancing adherence and SVR in PWIDs.** 75 subjects will receive Zepatier will be randomized to take medications by either treatment as usual (self-administration), automated directly observed therapy (a-DOT), or a-DOT with gamification (25 subjects in each arm). Those in the a-DOT arm will be observed taking their Zepatier dose by the smart-phone based interface. We hypothesize that adherence and SVR will be higher in a-DOT versus TAU subjects, and that SVR in a-DOT arm will be equivalent to SVR seen in registration trials.
- 2. To evaluate the feasibility and acceptability of a-DOT to both participants and HCV providers in tracking longitudinal patterns of adherence and providing adherence feedback in real-time.** We hypothesize that a-DOT will be highly acceptable to both participants and medical providers.
- 3. To determine whether gaming features added to the aDOT platform enhance adherence compared to standard aDOT.** For the 25 subjects randomized to the aDOT + gamification arm, subjects will compete with other subjects within this arm for modest cash incentives. Those with highest levels of adherence measured at monthly research visits compared to their peers will earn additional incentives.

4. To determine the impact of ongoing drug use (cocaine, opiates, or benzodiazepenes) and on HCV virologic outcomes in subjects receiving Zepatier by aDOT. We hypothesize that ongoing drug use during HCV treatment will not be associated with adherence in subjects randomized to a-DOT.

B. APPROACH

B.1. Preliminary Studies

B.1.1. Overview of the research team. [name] has focused on defining optimal models of HCV care for PWIDs over the last 15 years, and is expert in treating HCV in PWIDs, methadone and buprenorphine-maintained patients, and active drug users.

Monitoring and improving adherence to antiviral therapy in real world settings requires methods that address varied challenges in treating high-risk populations. While accuracy is paramount, cost, ease of deployment, desirability, scalability, privacy, and flexibility are also important for ensuring wide-scale utility.

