In our previous DOT study, mean adherence in the mDOT group was 87% (SD=12%, n=21), and mean adherence in the TAU group was 77% (SD=20%, n=19) which translates into a standardized effect size or Cohen's d = 0.6. Based on this effect size, the power of the mixed effects linear model for the repeatedly measured continuous adherence outcome will be greater than 80%, even if anticipated ICC is as high as 0.5.

We will determine the proportion (and Wald or exact 95% CI) of subjects randomized to aDOT arm (n=50) who achieve SVR. For example, if SVR is achieved in 70% of the 50 study participants, the 95% confidence interval around that proportion will be: 57%, 83%. If SVR is achieved in 80%, the 95% confidence interval will be: 69%, 91%. If SVR is achieved in 90%, the 95% confidence interval will be: 82%, 98%. The overall SVR for all subjects will be compared to historical controls to demonstrate feasibility of treating real-world injection PWIDs with Zepatier-based regimens. Although our study lacks power to definitively answer the question of whether a-DOT improves SVR, our study will provide an estimated effect size to be used in future R01-funded studies examining the efficacy of a-DOT.

We used power calculations for Fisher's exact test (with 80% power and 5% significance level in a two-tailed test) to find the minimum detectable difference between the percentage of "adherent" subjects in the favorable group (e.g. not actively using drugs) vs. unfavorable group (e.g. actively using drugs). We would be able to find that a characteristic is significantly associated with adherence if there are 71% "adherent" subjects in the favorable group vs. no more than 41% "adherent" subjects in the unfavorable group (3.55 in terms of odds ratio). When using adherence as a continuous measure, we will have greater power to show correlations between continuous predictor variables and adherence. We calculated the minimum detectable correlation coefficient with 80% power and 5% significance level to be 0.33 which represents a small to medium correlation effect size. Therefore, we expect to have sufficient power to detect some associations that are likely to exist.

We will determine an effect size with respect to the outcome of adherence in the aDOT + gamification arm vs. a-DOT arm which will inform future R01 interventions.

C. References

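### The multivariable logistic model for adherence takes its terms from univariate results, so the Aim 4 drug-use estimate may be dropped, or kept mainly when it is exaggerated

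*Combined protocol and SAP*

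**What the plan says.** Aim 4 states its hypothesis as a null: "We hypothesize that ongoing drug use during HCV treatment will not be associated with adherence in subjects randomized to a-DOT".

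Section B.10 (Analytic plan) takes this up in three steps. First comes an unadjusted comparison: "For subjects randomized to the a-DOT arm, association between active drug use during treatment and the continuous adherence will be tested", by a t or Wilcoxon test. Next, dichotomous adherence (the 80% cut-off) is compared across categorical variables by chi-square and Fisher tests. Then: "We will conduct multivariate logistic regression analyses based on findings from the univariate analysis". The same sentence concedes the limit: the investigators "recognize that our modest sample size will limit such models".

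B.10 states no univariate threshold, no maximum number of terms and no penalisation for these models. It does not say whether drug use is retained whatever its univariate result. It also does not repeat, for the logistic models, that only a-DOT subjects are analysed. The rule is separate from the one at the start of B.10, which concerns variables unbalanced between arms.

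**The concern.** Drug use is the question of Aim 4, not one covariate among many. If its place in the model depends on its univariate result in the same small sample, two things can happen. It may fail the screen, and then no adjusted estimate or confidence interval is reported. Because the hypothesis is one of no association, that absence can be misread as support. Or it may pass, and then the reported odds ratio comes from the trials in which the estimate happened to be large. Other variables with no true effect can enter by the same route and be described as predictors of adherence.

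**Working it through.** **Inputs from the documents.** The a-DOT group is 50 (B.10: "subjects randomized to aDOT arm (n=50) who achieve SVR"). The trial is 75 (B.2: "randomized to either aDOT (n=25), aDot + gamification (n=25), or TAU (n=25"). Assumed a-DOT adherence is 80% (B.10: "if we conservatively assume that 80% of subjects in the a-DOT will achieve" the cut-off), with 50% under usual treatment. B.10's detectable difference for a predictor such as drug use is 71% v 41% adherent, odds ratio 3.55, with 80% power at two-sided 5% by Fisher's test.

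**Assumptions not in the documents.** Screening thresholds of 0.05 and 0.20; drug-use splits (non-users/users) of 25/25 and 35/15; a true odds ratio of 2 for non-adherence; no dropout.

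**The plan's own figure.** (0.71/0.29)/(0.41/0.59) = 3.52, which agrees with 3.55 within rounding. The power does not reproduce at the trial's sizes: Fisher power is 0.51 at 25/25 and 0.71 at 37/38, and 80% needs about 48/48. The documents do not give the group sizes behind this figure.

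**Events.**
- a-DOT at 80% adherent: 50 × 0.20 = 10 non-adherent (95% binomial range 5 to 16).
- The 71% v 41% scenario with equal groups: mean adherence (71 + 41)/2 = 56%, so 50 × 0.44 = 22.
- All 75 subjects: 50 × 0.20 + 25 × 0.50 = 22.5, or 30%.

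**What a screen demands with 10 non-adherent.** At 25/25, 8 users v 2 non-users gives Fisher p = 0.074. The smallest passing table is 9 v 1, with odds ratio (9 × 24)/(1 × 16) = 13.5. At 35/15 it is 6 of 15 users v 4 of 35 non-users (p = 0.048), with odds ratio (6 × 31)/(4 × 9) = 5.2. A true odds ratio of 2 cannot pass without being overestimated.

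**Exact enumeration of all 2×2 tables.** The true odds ratio is 2, and overall adherence is held at the stated level. Each odds ratio is computed with 0.5 added to every cell, and the mean is geometric over the tables that pass.

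| Non-adherent | Split | p≤0.05: retained, mean OR | p≤0.20: retained, mean OR | Always kept |
|---|---|---|---|---|
| 20% of 50 | 25/25 | 9%, 8.0 | 27%, 4.7 | 2.0 |
| 20% of 50 | 35/15 | 15%, 6.1 | 34%, 4.1 | 2.0 |
| 44% of 50 | 25/25 | 17%, 4.8 | 36%, 3.6 | 2.0 |
| 44% of 50 | 35/15 | 14%, 5.4 | 34%, 3.8 | 2.0 |
| 30% of 75 | 38/37 | 25%, 3.9 | 49%, 3.0 | 2.0 |
| 30% of 75 | 52/23 | 22%, 4.0 | 49%, 3.0 | 2.0 |

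A separate simulation at n = 75 gave median selected odds ratios of 3.5 (p<0.05) and 2.8 (p<0.20). Over the 22-event and 75-subject settings, then, the typical selected odds ratio runs from about 2.8 to 5.4.

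**False predictors.** B.10's balance check names six variables besides drug use. Taking these as independent null candidates, the chance that at least one enters is 1 − 0.95^6 = 26% at 0.05 and 1 − 0.80^6 = 74% at 0.20. Simulation, which allows for the discreteness of the tests, gives 21% and 67%.

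**Precision if drug use is always kept.** With 10 non-adherent split 5/5 at 25/25, SE(log OR) = √(1/5 + 1/20 + 1/5 + 1/20) = 0.707. The 95% CI around an odds ratio of 1 is exp(±1.96 × 0.707), or 0.25 to 4.0. At 35/15 with 7/3 it is 0.22 to 4.5.

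**The case against.** The text can be read more kindly. Drug use is the named exposure in the same paragraph, so the authors may intend to keep it and choose only the other covariates from univariate results. A reader might infer that drug use enters only when exaggerated and is dropped otherwise. The documents do not support that: no screen on drug use is stated, and with p≤0.20 and a true odds ratio of 3.55, 14-17% of entries at 10 events are not exaggerated. This part of the objection stands.

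The unadjusted drug-use tests involve no selection, so an unselected drug-use result exists whatever the model does. The plan concedes the sample-size limit, and B.9.5 describes a pilot. These points also stand. However, the logistic model is the only adjusted drug-use analysis B.10 describes for a-DOT subjects, and the concession adds no safeguard.

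The figure of 10 events borrows the arm-comparison assumption, and the model's population is not fixed. A detectable correlation of 0.33 needs about 70 subjects (at 50 it is 0.39), which hints that predictor analyses may use nearly everyone. With more events the inflation shrinks but remains.

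A reader might also infer that false predictors will appear. That is a risk whose size depends on the threshold and the number of candidates, not a certainty.

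Lastly, forcing drug use in does not cure imprecision. That is true, but the reported interval would then show it.

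**Conclusion.** The concern holds in a limited form. B.10 lets univariate findings shape the adherence model and does not protect the Aim 4 exposure from that selection. If drug use is screened, a true odds ratio of 2 would typically be reported as about 4 to 8 with 10 events, and as about 2.8 to 5.4 with 22 events or all 75 subjects. In at least half of trials, and in most at the stricter threshold, no adjusted estimate would be reported at all.

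These sizes rest on assumed thresholds, drug-use splits and a true odds ratio of 2. They describe unadjusted 2×2 odds ratios rather than full multivariable output. The documents do not establish that drug use must pass a screen, that the model is confined to a-DOT subjects, or that Aim 4 lacks any unselected result. The point deserves correction because Aim 4 predicts no association, and a dropped term is easily mistaken for evidence of that.

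**What to change.** Replace the model-building sentence in B.10 with wording to this effect:

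- Drug use stays in the adherence model whatever its univariate p-value.
- At most one or two covariates are fixed in advance, and none is selected on univariate results. Candidates are a-DOT v a-DOT + gamification arm, since Aim 3 asks whether gamification changes adherence, or recruitment setting. The choice is the sponsor's.
- The analysis population (a-DOT subjects or all subjects) is named.
- The 80% outcome is analysed by Firth-penalised logistic regression, and continuous adherence by linear regression.
- The drug-use estimate and its 95% CI are reported whatever the p-value, with a statement that a wide interval (about 0.25 to 4.0 with 10 events) does not support the hypothesis of no association.

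The cost is a change of SAP wording and standard software, with no extra subjects or visits. The downside is that fewer exploratory predictors enter the multivariable model. They can still be tabulated one at a time as unadjusted, exploratory results.
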